4.1 General description of the study

Phase I clinical study, controlled, non-comparative, open, single-center

4.2 Justification of the study design

Study design (clinical trial) is considered the highest standard of data quality when exploring the effect of an intervention. The drug development phase (Phase I) corresponds to the study's objective, which is to evaluate safety and tolerability. Therefore, the intervention time is short and the required sample size is smaller than that of an efficacy clinical trial. Blinding was not considered in the study because there will only be one treatment group.

4.3 Expected duration

The total duration of the study, from the first patient visit to the final report, is estimated to be 5 months, with a 4-month recruitment period.

The approximate duration of each subject in the study is 10 days.

5. Study population

5.1 Eligibility criteria

5.1.1 Inclusion criteria

- Be clinically healthy
- Have the ability to voluntarily grant signed informed consent
- Be able and willing to comply with scheduled visits, treatment plan, and other study procedures
- Be between 18 and 45 years old.
- Women of childbearing potential must ensure continued use (started \geq 30 days prior to signing the ICF) of a hormonal contraceptive method or intrauterine device (IUD) during the study period.
- Have a best-corrected visual acuity of 20/30 or better in both eyes.
- Have vital signs within normal parameters.
- Have an intraocular pressure \geq 10 and \leq 21 mmHg.

5.1.2 Exclusion criteria:

- Be a user of topical ophthalmic products of any kind.
- Being allergic to naphazoline or having a history of intolerance to nasal decongestants or ocular vasoconstrictors.
- Have a history of a suspected diagnosis of primary angle closure, primary angle closure, or angle-closure glaucoma.
- Having iridotomies or waiting for iridotomies.
- Have conjunctival hyperemia grade 3 and 4 on the Efron scale.
- Have ocular surface staining with a value equal to or greater than 3 on the SICCA scale in either eye.
- Being a user of medications or herbal products, by any other route of administration.
- For women: be pregnant, breastfeeding, or planning to become pregnant during the study period.
- Having participated in clinical research studies 90 days prior to inclusion in this study.
- Having previously participated in this same study.
- Be a contact lens user who cannot discontinue use during the study.
- Having a history of any chronic-degenerative disease, including diabetes and high blood pressure.
- Present inflammatory or infectious disease, active at the time of entering the study.
- Present unresolved injuries or traumas at the time of entering the study.
- Have a history of any type of eye surgery
- Having undergone non-ophthalmological surgical procedures in the last 3 months.

5.2 Criteria for elimination and/or substitution of subjects

5.2.1 Elimination criteria

- Withdrawal of informed consent.
- Major deviation from the protocol that could impact the integrity of the results.
- Presentation of an adverse event, whether or not related to the investigational product, which, in the opinion of the PI and/or the sponsor, could affect the subject's ability to safely continue the study procedures.
- Non-tolerability or hypersensitivity to any of the compounds used during the tests.
- Non-tolerability or hypersensitivity to the investigational product.

5.2.2 Subject substitution

The sponsor, with prior authorization from the research ethics committees, may decide to replace subjects who withdraw their FCI or those who are lost to follow-up, if it is necessary to balance the study groups so that they are evaluable.

5.3 Scrutiny failures

A screening failure is defined as a participant who agrees to participate in the study, giving their consent, but who is not assigned to a treatment group; that is, they do not enter the study. The following information regarding screening failures must be reported, at a minimum:

- Demographic data.
- Details of the counting failure (specify whether due to eligibility criteria, which one, or some other reason for the failure).
- Presence of serious adverse events during the scrutiny.

The above is necessary to comply with the CONSORT guidelines (*Consolidated Standards of Reporting Trials*) for the publication of results or to respond to potential questions from regulatory authorities.

5.4 Recruitment and retention strategies

The subject's participation in the study lasts approximately 10 days, during which they will attend four visits in total, corresponding to the baseline, first, second, and final visits. Strategies to improve subject retention include, but are not limited to:

- Clearly report the objectives of the study.
- Make calls or send text messages to remind yourself of appointments or activities to do.
- Provide a printed calendar and ID card to remind you of upcoming appointments and activities, as well as their estimated duration.

- Systematic organization of the study procedures, so that the subject does not stay longer than necessary during his visit.
- Minimize subject wait times.

All materials to be delivered to the subject or recruitment strategies implemented by the center will be submitted for approval by the corresponding committees.

5.5 Procedure in case of early discontinuation

For this protocol, early discontinuation is defined as those subjects who were assigned the PI, who at some point were active subjects in the study, but their final evaluation could not be completed.

If the subject does not complete their participation due to withdrawal of consent or a major deviation, the last visit at which their withdrawal was determined will be considered their final visit. Subjects withdrawn due to the presence of AEs will continue the follow-up as determined until their AE is resolved.

In cases where the participating subject does not attend their appointment, the research site will call to determine the reason and will attempt to schedule a new appointment within the established window or an unscheduled appointment. If an appointment cannot be scheduled, the subject will be considered lost to follow-up, and the presence of adverse events and the reason for discontinuing the study will be asked as minimum data.

5.6 Subject identification

Study subjects will be identified by a number and the initials of their name.

The initials of the subject of study will be obtained starting with the first letter of the name, followed by the first letter of the first surname and the first letter of the second surname, obtaining a maximum of three letters. In case the person has two names or a compound surname, the first letter will always be used.

Example:

[figure not shown]
TO. [name] B. [name]
to. Initials: AMC b. Initials: JDO

During the counting stage, you will be assigned a participant number consecutively, using 3 consecutive digits.

Once the subject has been selected, they will be assigned a number that will identify them throughout the study. This code will consist of eight numbers in the following order from left to right:

- three digits of the molecule under study according to the name given by the sponsor.
- two digits corresponding to the research center number.
- three digits of the consecutive number assigned to its inclusion in the research center.

Example of assigned number:

6. Investigational product and treatment

6.1 Managed Products

6.1.1 Investigational Product

- PRO-185. Naphazoline 0.03% and hypromellose 0.2%. Solución oftálmica. Laboratorios Sophia, S.A. de C. V., Zapopan, Jalisco, Mexico.
- Route of administration: Ophthalmic.

6.1.2 Dose of the investigational product

- Dosage: 1 drop 4 times a day in both eyes (AO).

6.1.3 Treatment with the investigational product

The investigational product will be administered at the conclusion of the baseline visit, and the subject will administer the drops approximately every 2-4 hours between drops, applying them a total of 4 times per day to each eye.

Baseline visits, 1, and 2, should be completed in the morning, before 11 a.m., to allow the patient more time to apply PRO-185 throughout the day. During visits 1 and 2, the patient will come to the clinic without having previously applied the investigational product. The first application will be considered the drop applied by the researcher during the visit. For visit 1, the patient will be required to apply the product three times after the visit has concluded. For visit 2, the patient will not need to apply the product again because the investigational product will have been returned to the researcher.

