2.3 Background on the investigational product

We do not have clinical studies of an ophthalmic solution containing naphazoline, hypromellose, and menthol. However, we have experience in clinical studies with naphazoline and hypromellose at higher concentrations than PRO-185, as well as in a preclinical safety and toxicity study of PRO-185 ophthalmic solution.

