7.5.9 Applying medication during visits

During patient visits, various medications or medical devices may be applied to the ocular surface for ophthalmological examination.

Examples:

- Tetracaine 0.5% ophthalmic solution, used to anesthetize the patient and facilitate measurement of intraocular pressure, application of dyes for staining, and placement of the gonioscopy lens.
- Ophthalmic solution of 0.8% tropicamide and 5% phenylephrine, used to dilate the pupil and better assess the posterior segment.
- PRO-185 ophthalmic solution, an investigational drug, applied at visits 1 and 2.
- Hypromellose 2% ophthalmic solution may be used by the Researcher for gonioscopy assessment.

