7.6.2 Study activity schedule

Table v. Study schedule

Procedures	Baseline visit		Visit 1		Visit 2		Final visit
	Day 1		Day 3 (+1)		Day 8		Day 10 (+1)
	Pre-TP	Post -	Pre -	Post-	Pre -	Post-	Without
	TP	Tx	Tx	Tx	Tx	Tx	treatment
FCI Signature	X						
Medical record	X						
Eligibility criteria	X						
Subject code assignment	X						
Adverse events	X	X	X	X	X	X	X
Heart rate	X	X	X	X	X	X	X
Respiratory rate	X		X		X		X
Blood pressure	X	X	X	X	X	X	X
Temperature (°C)	X		X		X		X
Urine pregnancy test	X						X
AVMC	X		X		X		X
Anterior segment evaluation	X	X	X	X	X	X	X
Pupillary diameter measurement	X	X	X	X	X	X	X
Eye stains	X	X	X	X	X	X	X
Intraocular pressure	X	X	X	X	X	X	X
Gonioscopy	X						
Pharmacological mydriasis (phenylephrine/tropicamide)	X						
Evaluation of the posterior segment	X		X		X		X
Application of PRO-185 during a visit			X		X		
Delivery of material for the subject		X					
Delivery of the study medication		X					

Procedures	Baseline visit		Visit 1		Visit 2		Final visit
	Day 1		Day 3 (+1)		Day 8		Day 10 (+1)
	Pre-TP	Post -	Pre -	Post-	Pre -	Post-	Without
	TP	Tx	Tx	Tx	Tx	Tx	treatment
Evaluation of concomitant medications	X		X		X		X
Adherence assessment			X		X		
Return of study medication						X	
Withdrawal from the subject's diary						X	

PRE-TP: prior to application of 0.8% tropicamide and 5% phenylephrine ophthalmic solution (TP Ofteno[®]), indicates that the checks will be performed prior to pharmacological mydriasis. Post-TP: post application of the TP Ofteno[®] solution, indicates that the checks will be performed with pharmacological mydriasis. Pre- Tx : pretreatment, indicates the checks to be performed before the application of the investigational medicinal product. Post-Tx : post-treatment, indicates the evaluations to be performed within 20-40 minutes after the application of the investigational medicinal product. ICF: informed consent form. BCVA: best corrected visual acuity.

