7.7.1 Baseline visit

- Consent signature informed
- General and ophthalmological clinical history taking
- Measurement of vital signs (temperature, blood pressure, heart rate, respiratory rate)
- Drug evaluation concomitants
- Measurement of best-corrected visual acuity
- Ophthalmological evaluation (before and after pupil dilation)
- Evaluation of pupil diameter
- Ocular staining with fluorescein and lissamine green
- Measurement of intraocular pressure
- Gonioscopy
- Review of eligibility criteria
- Event evaluation adverse
- Pupil dilation
- Delivery of the investigational product

7.7.2 Visit 1

- Pre-application procedures for the investigational product
 - o Measurement of vital signs (temperature, blood pressure, heart rate, respiratory rate)
 - o Drug evaluation concomitants
 - o Measurement of best-corrected visual acuity
 - o Assessment ophthalmological
 - o Evaluation of pupil diameter
 - o Ocular staining with fluorescein and lissamine green
 - o Measurement of intraocular pressure
 - o Review of continuation criteria
 - o Event evaluation adverse
- Post-application procedures for the investigational product
 - o Measurement of vital signs (blood pressure and heart rate)
 - o Measurement of best-corrected visual acuity
 - o Assessment ophthalmological
 - o Evaluation of pupil diameter
 - o Ocular staining with fluorescein and lissamine green
 - o Measurement of intraocular pressure
 - o Review of continuation criteria
 - o Event evaluation adverse

7.7.3 Visit 2

- Pre-application procedures for the investigational product
 - o Measurement of vital signs (temperature, blood pressure, heart rate, respiratory rate)
 - o Drug evaluation concomitants
 - o Measurement of best-corrected visual acuity
 - o Assessment ophthalmological
 - o Evaluation of pupil diameter
 - o Ocular staining with fluorescein and lissamine green
 - o Measurement of intraocular pressure
 - o Review of continuation criteria
 - o Event evaluation adverse
- Post-application procedures for the investigational product
 - o Measurement of vital signs (blood pressure and heart rate)
 - o Measurement of best-corrected visual acuity
 - o Assessment ophthalmological
 - o Evaluation of pupil diameter
 - o Ocular staining with fluorescein and lissamine green
 - o Measurement of intraocular pressure
 - o Review of continuation criteria
 - o Event evaluation adverse
 - o Return of the research product

- Return of the subject's diary

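### Protocol and SAP disagree on whether PRO-185 is applied and measured at baseline, so readings taken under dilating drops could be analysed as post-PRO-185 readings

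*Protocol*

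**What the plan says.** Protocol 6.1.3 places the start of treatment on Day 1: "The investigational product will be administered at the conclusion of the baseline visit". The same sentence goes on to have the subject instil the drops. For visits 1 and 2 only, the section adds that the subject arrives undosed that day and that "The first application will be considered the drop applied by the researcher during the visit".

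Elsewhere the protocol gives no application at baseline. Section 7.5.9 lists "PRO-185 ophthalmic solution, an investigational drug, applied at visits 1 and 2". The row "Application of PRO-185 during a visit" in 1.3 and Table v is marked at visits 1 and 2 and blank in both baseline columns. Section 7.7.1 ends with "Delivery of the investigational product", and 7.5.11 describes handing over the bottle and explaining its use.

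The protocol's second baseline column is Post-TP, which "indicates that the checks will be performed with pharmacological mydriasis". The label Post-Tx, which "indicates the evaluations to be performed within 20-40 minutes after the application of the investigational medicinal product", belongs to visits 1 and 2.

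SAP Table 1 differs. It heads the two baseline columns Pre-Tx and Post-Tx and marks an application of the medicine at baseline as well as at visits 1 and 2. It marks heart rate, blood pressure, pupil, staining and IOP in the baseline Post-Tx column. It has no row for dilation, and its footnote defines Post-Tx as 20–40 minutes after the investigational drug.

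**The concern.** The same cells of the visit schedule carry two meanings. Under the protocol they hold readings after the dilating drops and before any PRO-185. Under the SAP they hold readings after PRO-185. An analyst working from the SAP could treat the baseline pair as a pre/post PRO-185 contrast. Protocol 7.4.5.4 attributes a pupil change above 2 mm to the product, and mydriasis is one of the five primary events, so that mistake could produce false primary events. Heart rate, blood pressure and IOP from the same column would be misattributed in the same way.

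The conflict also leaves open what the 20-minute results describe. The specific objectives for IOP, heart rate and blood pressure refer to 20 minutes after application, and 10.1.2 extends this to all five primary events relative to the initial value. Under the protocol schedule those effects are observed only in subjects who have already been dosing for at least two days. A subject who stops before visit 1 is in the safety population (at least one dose, 10.3.2.1) but has no scheduled 20-minute reading, and 10.4 plans no imputation.

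**Working it through.** The plan gives no figure to reproduce. The check sets the passages side by side and then counts the consequences.

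**1. Baseline visit, by source**

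| Source | PRO-185 applied at baseline? | Second baseline column |
|---|---|---|
| Protocol 1.3 and Table v | No mark; marked at visits 1 and 2 | Post-TP, under dilation |
| Protocol 7.5.9 | Names visits 1 and 2 only | – |
| Protocol 7.5.11 | Bottle given, dosing explained | – |
| Protocol 7.7.1 | Delivery only | Eye examination before and after dilation |
| Protocol 6.1.3 | Administered at the end of the visit; person and place not stated | No checks described |
| SAP Table 1 | Marked, as at visits 1 and 2 | Post-Tx, 20–40 minutes after the drug; no dilation row |

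Heart rate, blood pressure, pupil, staining and IOP are marked in the second baseline column of both schedules. The SAP's application row has three marks and the protocol's has two, so a column shift in the extracted table would not explain the difference.

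**2. Effect of reading Post-TP as Post-Tx**

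Inputs: 22 planned subjects (Protocol 10.1.2), an event limit of 20% (Protocol 3.2) or 10% (SAP 3.2), and the 2 mm rule (Protocol 7.4.5.4).

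- 20% limit: 0.20 × 22 = 4.4. Four subjects give 4/22 = 18.2% and five give 5/22 = 22.7%, so five exceed it.
- 10% limit: 0.10 × 22 = 2.2. Two subjects give 2/22 = 9.1% and three give 3/22 = 13.6%, so three exceed it.

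The documents do not say how far the dilating drops widen the pupil. If a fraction d of subjects change by more than 2 mm, the false count is 22 × d. This is 0 at d = 0, 11 at d = 0.5 and 22 at d = 1. The protocol's limit is passed once d is at least 5/22, about 0.23.

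**3. Applications before the first post-dose reading, if the protocol schedule is followed**

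Assume four applications per eye on Day 1 and full adherence.

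- Visit 1 on Day 3: 4 + 4 = 8 applications come first, and the 9th is the first one measured.
- Visit 1 on Day 4: 4 + 4 + 4 = 12 come first, and the 13th is the first one measured.
- Whole course: 7 full days × 4, plus the single drop at visit 2, is 29 per eye, of which 2 are followed by 20–40 minute checks.

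If only one to three applications were made on Day 1, the counts fall to 5–7 (Day 3) or 9–11 (Day 4). If SAP Table 1 were followed instead, the baseline application would be measured and the measured applications would be 3 of 29.

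**The case against.** The strongest reply is that the protocol is internally workable. Section 6.1.3 can be read as dosing that starts once the visit is over, with the subject instilling the drops. That fits a blank in a row about application during a visit, and it fits 7.5.9 and 7.7.1. A reader might infer a flat contradiction inside the protocol, but the text does not force one. What stands is that 6.1.3 does not say who gives the first drop or where.

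Second, Protocol 3.2 and 10.3.2.1 already confine the acute comparisons to visits 1 and 2, and no section uses the words first application in stating an objective. A reader might infer that the plan claims first-dose safety outright; it does not. This also gives some protection against misuse of the baseline column. The protection is incomplete: SAP 6.2.1 does not restrict the analysis to those visits, and 7.4.5.4 compares the baseline visit with any other pupil measurement.

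Third, leaving PRO-185 out of the baseline measurements may be deliberate, because readings after the dilating drops would be hard to attribute to it. That is reasonable, although the protocol gives no such rationale. It supports the protocol's labels and does nothing for the SAP's.

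Two further inferences go too far. One is that the first dose is never measured: that is true of the protocol schedule only, since SAP Table 1 shows post-dose readings at baseline. The other is that this is the first clinical use of the combination. Section 2.3 says only "We do not have clinical studies of an ophthalmic solution containing naphazoline, hypromellose, and menthol", and 2.5.1 and 2.7 refer to similar menthol products on other markets.

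**Conclusion.** The point holds as a conflict between the protocol and SAP schedules, with a gap in 6.1.3. Table v and SAP Table 1 cannot both describe the baseline visit.

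The consequence depends on which schedule is carried out. If data are collected as Post-TP and analysed as Post-Tx, dilating-drop effects enter the PRO-185 results. Five of 22 affected pupils would then be enough to pass the protocol's limit. How many would be affected is not given in the documents, so this is a stated risk and not an estimate. If the protocol schedule is followed and labelled correctly, the results are sound for what they measure, which is the effect 20–40 minutes after a drop in subjects already treated for at least two days. The counts of about 8 or 12 prior applications rest on four applications on Day 1 and full adherence.

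Whether a first-exposure reaction would differ from a later one is not established by the documents. No view is taken on which dosing arrangement is right.

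**What to change.** Reconcile Protocol 6.1.3, 7.5.9, 7.5.11, 7.7.1, 1.3/Table v and SAP Table 1 so that they state once whether PRO-185 is applied at baseline, where and by whom the first application is given, and what the second baseline column measures.

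If that column is Post-TP, relabel it in SAP Table 1, add the dilation row, and state in SAP 6.2.1 that its readings are excluded from the pre/post PRO-185 comparisons and from all event counts, including the 2 mm pupil rule.

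If no reading follows the first application, say in the objectives, in 10.1.2 and in the report that the 20-minute effects were measured only at visits 1 and 2, after at least two days of dosing.

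The cost is wording in both documents and a matching label in the data collection form. The downside is a narrower claim about acute effects. Sample size and visits are unchanged if the protocol schedule stands.

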6.2 Storage and handling of the investigational product at the study center

Delivery will be made via a courier service contracted by the sponsor, specifically selected for this purpose, to the address of the research center in accordance with the study plan.

Reception will be carried out by the assigned research team staff. They must verify the condition of the primary packaging (box). If it shows alterations or defects in its integrity that, in their judgment, could have damaged the contents, they must report this to the sponsor. If the package shows no significant defects, they will proceed to open it.

Inside the shipment, you must locate the receipt and temperature *data logger*. You must verify that the recorded temperature meets the specifications for its transport and storage. You will verify the contents (PI) with what is reported on the document. If the document matches the contents, you will sign the receipt and send it to the sponsor. If not, you will notify the sponsor.

Storage and safeguarding are the responsibility of the research center. The medication must be kept in a secure area with restricted access.

Storage temperature should be 2° to 30°C.

Upon receipt at the center and until the PI is out of stock, the research center is required to review the PI storage conditions daily and manually record the temperature recorded by the *data logger* (current, minimum, and maximum temperatures) in the designated format . These data will be reviewed by the clinical monitor during their monitoring visits, based on the records stored in the data logger's memory .

In the event of material loss, this must be documented in the input and output log along with a clear description of the mechanism by which the loss occurred.

Upon completion of the protocol, all study materials will be retrieved by the sponsor as part of the closing visit. The final return of materials will be made by the principal investigator or the person designated by the principal investigator to return materials at the end of the study.

The sponsor reserves the right to initiate civil and criminal action against the principal investigator in the event of undocumented material missing at the end of the study.

